4.0 Objectives

Phase 1:

Primary Objectives

1. To determine the maximum tolerated dose (MTD) of the combination of lenalidomide and thalidomide and dexamethasone (LTD) in patients with relapsed/refractory multiple myeloma (RRMM).

Secondary Objectives

1. To determine the Overall response rate (ORR)
2. To determine the Time to progression (TTP)
3. To determine the Progression free survival (PFS)
4. To determine the Time to best response

Phase 2:

Primary objective:

1. To determine the overall (CR + VGPR+ PR) response rate of the combination after 4 cycles of therapy.

Secondary Objectives

1. To determine the CR, VGPR
2. To determine the Time to progression (TTP)
3. To determine the Progression free survival (PFS)
4. To determine the Time to best response
5. To assess the safety of the combination of LTD in patients with RRMM.
6. Time to next therapy
7. Symptom measurement - Multiple-symptom assessment tool

5.1 **Selection of Patients**

5.2 **Inclusion Criteria**

1. Understand and voluntarily sign an informed consent form.
2. Age \geq 18 years at the time of signing the informed consent form.
3. Relapsed/refractory MMM with measurable levels of myeloma paraprotein in serum (\geq 0.5 g/dl), urine (\geq 0.2 g excreted in a 24-hour collection sample), or abnormal free light chain (FLC) ratio.
4. Serum Creatinine \leq 2.5 mg/dl
5. Females of childbearing potential (FCBP)[†] must have a negative serum or urine pregnancy test with a sensitivity of at least 50 mIU/mL within 10-14 days prior to and again within 24 hours of starting lenalidomide and must either commit to continued abstinence from heterosexual intercourse or begin TWO acceptable methods of birth control, one highly effective method and one additional affective method AT THE SAME TIME, at least 28 days before she starts taking lenalidomide. FCBP must also agree to ongoing pregnancy testing. Men must agree to use a latex condom during sexual contact with a female of childbearing potential even if they have had a successful vasectomy. All patients must be counseled at a minimum of every 28 days about pregnancy precautions and risks of fetal exposure. See Appendix A: risks of Fetal Exposure, Pregnancy Testing Guidelines and Acceptable Birth Control methods.

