6.3.1 Study Duration

Patients who attain a CR/VGPR/PR may elect to stop treatment at any point after cycle 2 and proceed to stem cell mobilization and transplantation. Patients who achieve less than a CR/nCR or patients, or who do not proceed to SCT, may receive up to 8 cycles of the combination therapy. Patients who progress will be removed from therapy. If a patient in CR/nCR/VGPR then patients receive up to 2 cycles beyond best response or up to 8 cycles at physician discretion and then proceed to maintenance therapy.

After 8 cycles, patients who have stable or responding disease to treatment and have an acceptable toxicity profile will be allowed to continue treatment on a maintenance schedule described below until disease relapse, unacceptable toxicity, withdrawal of consent or no further clinical benefit is experienced. Doses of thalidomide, lenalidomide, or dexamethasone may be interrupted or reduced in an attempt to manage toxicity at physician discretion.

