6.7 On-study evaluations

Subjects who meet eligibility criteria will be enrolled into the study, and will be assigned a patient number.

Cycle one patients will be followed weekly on Cycle 1, Day 8, 15, 22 (+/- 3 days):

- Clinical laboratory tests: Blood chemistry [sodium, potassium, chloride, CO₂, calcium, magnesium, phosphorus, blood urea nitrogen (BUN), creatinine, glucose, albumin, total protein, alkaline phosphatase, total bilirubin, aspartate transaminase (SGOT/AST), glutamic pyruvic transaminase (SGPT/ALT), lactate dehydrogenase (LDH)
- Hematology: hemoglobin, hematocrit, white blood cell (WBC) count and differential, and platelet count.
- Symptom directed physical examination/vitals

Day 1+/- 7 days of each cycle of therapy (starting with cycle 2):

- Standard myeloma restaging studies including SPEP, UPEP, Free Light Chain measurements (SIFE, UIFE and Bone Marrow biopsy will be done at time of suspected complete remission to document complete remission). MRI and skeletal surveys will be done as clinically indicated to follow the disease.
- Directed neurologic examination will be performed, and questioning for symptoms of paresthesia and numbness.
- Physical Examination
- Clinical laboratory tests: Blood chemistry [sodium, potassium, chloride, CO₂, calcium, magnesium, phosphorus, blood urea nitrogen (BUN), creatinine, glucose, albumin, total protein, alkaline phosphatase, total bilirubin, aspartate transaminase (SGOT/AST), glutamic pyruvic transaminase (SGPT/ALT), lactate dehydrogenase (LDH)
- Hematology: hemoglobin, hematocrit, white blood cell (WBC) count and differential, and platelet count.
- 12 lead EKG
- Patients will be evaluated for AEs at each visit with the NCI CTCAE v3.0 used as a guide for the grading of severity.
- Multiple-symptom assessment tool (also known as the MDASI).
- Blood sample for Serum Cytokines every even cycle.

An unscheduled visit can occur at any time during the study. Source must be maintained for these unscheduled visits.

Multiple-symptom assessment tool (Also known as MDASI)

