End-of-Study Visit

If you go off study for any reason, you will have an end-of-study visit. This is usually done about 30 days after the last dose of the study drugs. At this visit, the following tests and procedures will be performed:

You will have a physical exam, including measurement of your vital signs and weight.

- Standard myeloma restaging studies including SPEP, UPEP, Free Light Chain measurements (SIFE, UIFE and Bone Marrow biopsy will be done at time of suspected complete remission to document complete remission)
- Clinical laboratory tests: Blood chemistry [sodium, potassium, chloride, CO₂, calcium, magnesium, phosphorus, blood urea nitrogen (BUN), creatinine, glucose, albumin, total protein, alkaline phosphatase, total bilirubin, aspartate transaminase (SGOT/AST), glutamic pyruvic transaminase (SGPT/ALT), lactate dehydrogenase (LDH)
- Hematology: hemoglobin, hematocrit, white blood cell (WBC) count and differential, and platelet count.

Follow-Up

Subjects who discontinue treatment for any reason, will be followed for 30 days. At treatment discontinuation, subjects will undergo a safety assessment approximately 30 days post the last dose of study drug.

Treatment is to be continued and patients will be followed until progression of disease. Patients eligible for and wishing to pursue stem cell transplant will receive at least 2 courses of therapy and will be followed until stem cell transplant, progression of disease, or treatment failure.

Treatment failure will be defined by progression of disease.

Response and progression will be evaluated in this study using the International uniform response criteria for multiple myeloma (Appendix D).

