	7							D U	D	D	D	D	D	D	S	S	S	S	S
	8								D U	D	D	D	D	D	D	D	S	S	S
	9									D U	D	D	D	D	D	D	D	D	S
	10										D U	D	D	D	D	D	D	D	D
	11											D U	D	D	D	D	D	D	D
	12												D U	D	D	D	D	D	D
	13													D U	D	D	D	D	D
	14														D U	D	D	D	D
	15															D U	D	D	D
	16																D U	D	D
	17																	D U	D
	18																		D U

E = Escalate to next higher dose

S = Stay at current dose

D = De-escalate to next lower dose

U = Current dose is unacceptable

Table 2. Operating characteristics

Scenario		Dose -1	Dose 1	Dose 2	Dose 3	Total # of Pts	Overall Toxicity
1	Toxicity Rate	0.4	0.55	0.65	0.65	17.568	0.535121
	Chance Selected	0.507	0.313	0.08	0.015		
	# of Pts Treated	5.799	6.069	5.322	0.378		
2	Toxicity Rate	0.05	0.1	0.4	0.6	18	0.366222
	Chance Selected	0.002	0.17	0.703	0.125		
	# of Pts Treated	0.432	3.321	11.718	2.529		
3	Toxicity Rate	0.05	0.1	0.15	0.4	18	0.287222
	Chance Selected	0	0.003	0.232	0.765		
	# of Pts Treated	0.012	0.48	7.164	10.344		
4	Toxicity Rate	0.2	0.35	0.55	0.6	17.979	0.435675
	Chance Selected	0.12	0.53	0.322	0.025		
	# of Pts Treated	2.073	7.074	7.941	0.891		
5	Toxicity Rate	0.05	0.1	0.15	0.2	18	0.184056
	Chance Selected	0	0.005	0.114	0.881		
	# of Pts Treated	0.03	0.315	5.991	11.664		
6	Toxicity Rate	0.5	0.6	0.65	0.7	17.16	0.574242
	Chance Selected	0.492	0.233	0.078	0.004		
	# of Pts Treated	6.216	5.283	5.388	0.273		

Phase II design:

During the phase II portion of the study, patients will be treated with lenalidomide, thalidomide, and dexamethasone in combination at the MTD established in the phase I portion. Furthermore, the patients treated at the MTD in the phase I portion of the study will be considered the first patients of the phase II portion. It is anticipated that at least 6 patients will be treated at the MTD in the phase I and will be later included in the analysis of the phase II portion.

Response will be assessed after 4 cycles of therapy.

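### Does the option to leave for transplant after cycle 2 leave the 4-cycle response rate, and the futility count built on it, undefined?

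*Combined protocol and SAP*

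**What the plan says.** Section 4.0 gives the phase II primary objective as the overall (CR, VGPR or PR) "response rate of the combination after 4 cycles of therapy". Section 7.0, under the phase II design, repeats the time point: "Response will be assessed after 4 cycles of therapy".

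Section 6.3.1 says that patients in CR, VGPR or PR "may elect to stop treatment at any point after cycle 2 and proceed to stem cell mobilization and transplantation". It adds: "Patients who progress will be removed from therapy". Section 6.7, under Follow-Up, says that transplant candidates receive at least two courses and "will be followed until stem cell transplant, progression of disease, or treatment failure". It then states: "Treatment failure will be defined by progression of disease". The end-of-study visit, also in section 6.7, includes myeloma restaging; on its timing the protocol says "This is usually done about 30 days after the last dose of the study drugs".

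Other passages bear on how to count:

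- Section 6.3 has response assessed at every cycle. Section 6.7 schedules restaging within 7 days of Day 1 of each cycle from cycle 2.
- Footnote a of the uniform response criteria requires two consecutive assessments, at any time before new therapy starts.
- Section 7.0 makes patients treated at the MTD in phase I the first patients of phase II. Its boundaries recommend stopping at 3 or fewer responses in 12, 7 or fewer in 24 and 11 or fewer in 36 patients evaluated.
- Section 6.12 defines a safety set. No efficacy set is defined.

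**The concern.** The primary endpoint names a time point, and the protocol allows the patients who do best to leave before it. Progressors leave too. Neither group is sure to have an assessment after cycle 4, and section 7.0 does not say what to do with them.

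Three counts are possible for a responder who leaves early: credited with the recorded response, scored as a non-responder, or left out as not evaluated. At the end of the trial, 18 responders among 36 patients, 4 of them early leavers, could be reported as 18/36 = 50%, 14/36 = 39% or 14/32 = 44%.

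The futility looks use the same count. With 5 responders among the first 12, the trial continues. If 2 of the 5 had gone to transplant and were scored as failures, the count would be 3/12, which meets the boundary. An active regimen could be stopped because its responders went to transplant. In an open-label, single-center trial, a counting rule settled after responses are known also invites a choice that favors one result.

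**Working it through.** **Inputs.** From section 7.0: response boundaries 3/12 and 7/24, toxicity boundaries 8/12 and 15/24, independence of response and toxicity, target response rate 0.5, toxicity 0.4. The looks at 36 patients are not early stops. The documents give no rate of transplant exit, so the fraction f of true responders who leave before the cycle-4 assessment is an assumption, shown from 2 to 30%.

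**Step 1: reproduce the plan's figure.** By exact binomial calculation,

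P(stop early) = 1 − P(responses >3 of 12 and >7 of 24) × P(toxicities <8 of 12 and <15 of 24).

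At response 0.5 the first factor is 0.914; at toxicity 0.4 the second is 0.934. So 1 − 0.914 × 0.934 = 0.147 from the unrounded factors, as the plan states. The method reproduces 19 of the 20 table entries. The exception (toxicity 0.55, response 0.5, printed 0.225, recomputed 0.459) is not used here.

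The boundaries 3, 7 and 11 also reproduce. With the Beta(3, 7) historical and Beta(0.6, 1.4) experimental priors, the posterior probability in the stopping rule is 0.916 at 3/12, 0.904 at 7/24 and 0.9002 at 11/36, against 0.823, 0.847 and 0.859 with one more response. They follow from the priors and the 0.90 cutoff and do not depend on how leavers are counted.

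**Step 2: what each count would do.** With true response rate 0.5, the rate seen by the rule is 0.5 if leavers are credited, 0.5(1 − f) if they are scored as non-responders, and 0.5(1 − f)/(1 − 0.5f) if they are left out and replaced.

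| f | Credited | Rate if non-responders | P(stop early) | Rate if left out | P(stop early) |
|---|---|---|---|---|---|
| 2% | 0.147 | 0.490 | 0.159 | 0.495 | 0.153 |
| 5% | 0.147 | 0.475 | 0.181 | 0.487 | 0.163 |
| 10% | 0.147 | 0.450 | 0.224 | 0.474 | 0.183 |
| 20% | 0.147 | 0.400 | 0.343 | 0.444 | 0.235 |
| 30% | 0.147 | 0.350 | 0.501 | 0.412 | 0.311 |

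If half of a 20% exit rate fell after cycle 4, f would be 10%. The example of 5/12 falling to 3/12 needs 2/5 = 40% of responders to leave early, which is beyond this range.

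**Step 3: which count the text supports.**

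- Early transplant exit under section 6.3.1 is open only to patients who have attained a response. Scoring them as failures would make response itself the route to a non-response.
- Response is assessed each cycle, so a response before exit is on record.
- The response criteria let confirmation fall at any time before new therapy. They do not tie it to cycle 4.
- Treatment failure is progression. A patient who has progressed by then is a non-responder, and no passage suggests removing that patient from the denominator.
- Section 7.0 brings the phase I patients treated at the MTD into the phase II analysis, so part of the denominator is stated.

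Together these give one natural count: responses recorded by the end of cycle 4 and before transplant, over all phase II patients, with progressors as failures. That is the credited column.

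**Step 4: who would lack a cycle-4 assessment.** Thalidomide is taken daily through each 28-day cycle. A patient who stops after cycle 3 has a last dose near day 84 and an end-of-study restaging near day 84 + 30 = 114. Cycle 5 Day 1 is day 4 × 28 + 1 = 113, so that restaging falls inside the 7-day window if transplant has not yet happened. The patients without one are mainly those who leave around cycle 2 or are transplanted before the visit.

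**The case for a change.** The strongest case for a change is that none of the passages in step 3 is tied to the 4-cycle rate. Sections 4.0 and 7.0 name a time point and do not say best response by that time. The count is both the primary result and the input to the futility looks, and a sentence in each section would cost little.

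The crediting reading also leaves a loose end. A patient who leaves right after cycle 2 and first responds at the restaging due on cycle 3 Day 1 has one qualifying assessment. Whether the end-of-study restaging can confirm that response depends on its falling before transplant, and the protocol does not guarantee that.

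Both points are true as descriptions of the text. The first shows that the rule is unstated; it does not make the literal reading plausible, since that reading would discard a response recorded under the protocol's own criteria. The second concerns few patients, and a fuller definition does not remove it: a rule that requires confirmation before new therapy can still score such a patient as a non-responder. Adding a window, a confirmation rule and an all-treated denominator would largely be a choice of estimand and would not correct an error.

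**Conclusion.** The plan leaves a detail unstated, and the remaining text supplies the answer that a competent analyst would use. Under it the effect is nil: P(stop early) at response 0.5 and toxicity 0.4 remains 0.147, and the boundaries 3, 7 and 11 are unchanged.

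An effect appears only if recorded responses are disregarded. Its size then depends on an exit rate that the documents do not give: 0.159 at 2% to 0.501 at 30% if leavers are scored as non-responders, and 0.153 to 0.311 if they are left out. The boundaries are worded as recommendations, so the investigators could see when a shortfall came from transplant exits.

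The conclusion rests on two judgments: that analysts will credit a response recorded before transplant, and that they will keep progressors in the denominator. The text supports both. What stays open is a response not yet confirmed at transplant exit, which matters for few patients and can be described when the results are reported. No change to the plan is needed.

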The overall response and toxicity will be monitored simultaneously using the Bayesian approach of Thall, Simon, Estey (1995, 1996) as extended by Thall and Sung (1998). Historical data on similar patients show an overall response rate (ORR) of 30% and toxicity rate of 30%. However, the information was down-weighted to reflect the same marginal ORR and toxicity rates in 2 patients. Independence was assumed between OR and toxicity. It is expected for the current trial that the three-drug combination will improve the ORR to 50% while the toxicity rate is maintained at 40%. A sample size of 36 ensures that, if the trial is not terminated early, a posterior 90% credibility interval for overall response rate will have width of 0.26 at most, under the assumption of a 50% of ORR. The probabilities of OR and toxicity for the historical data are modeled by beta distributions ($Beta(3, 7)$ and $Beta(3, 7)$, respectively). The prior probabilities of OR and toxicity for the experimental regimen are also modeled by beta distributions ($Beta(0.6, 1.4)$ and $Beta(0.6, 1.4)$, respectively), which have the same a/b (a and b denote the parameters for a $Beta$ distribution) ratio as the beta distributions for the historical data. Denoting the historical probabilities of overall response rate and toxicity rate by $\{p(OR,H), p(TOX,H)\}$, the following decision criteria will be applied:

- 1) Let E correspond to the experimental treatment, stop if $\text{Prob}\{p(OR,H) + \delta_{OR} > p(OR,E) | \text{data}\} > 0.90$, where $\delta_{OR} = 0.20$
- 2) Stop if $\text{Prob}\{p(TOX,H) + \delta_{TOX} < p(TOX,E) | \text{data}\} > 0.85$, where $\delta_{TOX} = 0.10$

Patients will be monitored according to the following stopping boundaries for overall response.

Number of patients evaluated	Recommend stopping if \leq OR observed
12	3
24	7
36	11

At the same time, patients will be monitored according to the following stopping boundaries for toxicity.

Among these number of patients	Recommend stopping if \geq toxicity observed
12	8
24	15
36	22

The operating characteristics are summarized in the following table (based on simulations from 10,000 trials).

True Toxicity Rate	True OR Rate	Prob(stop the trial early)
0.1	0.3	0.654
	0.4	0.296
	0.5	0.086

	0.6	0.016
	0.7	0.002
0.25	0.3	0.655
	0.4	0.298
	0.5	0.089
	0.6	0.019
	0.7	0.005
0.4	0.3	0.677
	0.4	0.343
	0.5	0.147
	0.6	0.082
	0.7	0.068
0.55	0.3	0.795
	0.4	0.583
	0.5	0.225
	0.6	0.417
	0.7	0.409

Analysis Plan

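### One Phase II operating-characteristics cell is impossible: early stopping at true toxicity 0.55 and true response rate 0.5 is printed as 0.225, but the stated boundaries give 0.459

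*Combined protocol and SAP*

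**What the plan says.** The Phase II part of Section 7.0 monitors response and toxicity together, with looks at 12, 24 and 36 patients.

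- Response: "Patients will be monitored according to the following stopping boundaries for overall response". Stopping is recommended at 3 or fewer responses in 12, 7 or fewer in 24, or 11 or fewer in 36.
- Toxicity: "At the same time, patients will be monitored according to the following stopping boundaries for toxicity". Stopping is recommended at 8 or more toxicities in 12, 15 or more in 24, or 22 or more in 36.
- Dependence: "Independence was assumed between OR and toxicity".
- Maximum size: "A sample size of 36 ensures that, if the trial is not terminated early", so an early stop is one at 12 or 24 patients.
- Expectation for the regimen: "the three-drug combination will improve the ORR to 50% while the toxicity rate is maintained at 40" percent.
- Design performance: "The operating characteristics are summarized in the following table (based on simulations from 10,000 trials").

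That table covers 20 combinations of true toxicity (0.1, 0.25, 0.4, 0.55) and true response rate (0.3 to 0.7). At toxicity 0.55 the printed early-stopping probabilities are 0.795, 0.583, 0.225, 0.417 and 0.409 as the response rate rises.

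**The concern.** The block looks wrong before any calculation. At a fixed toxicity rate, a better response rate can only make a stop for poor response less likely, so the column should fall from top to bottom. The other three blocks do. This one drops from 0.583 to 0.225 and then rises to 0.417.

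The affected cell is the only one in the table that pairs the expected 50% response rate with toxicity above the 40% the plan expects. It therefore shows how often the toxicity rule would act when efficacy is as good as hoped, which is a main reason for monitoring both outcomes together. A reader who takes 0.225 at face value would conclude that a regimen with 55% toxicity goes on to the full 36 patients in more than three trials out of four.

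**Working it through.** **Inputs, all from Section 7.0, Phase II design.** Response boundary: at most 3/12, at most 7/24. Toxicity boundary: at least 8/12, at least 15/24. Response and toxicity independent. Early stop means a stop at 12 or 24. True response rate 0.5; true toxicity rate 0.55.

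**Method.** Treat each outcome as a binomial count accumulated in two groups of 12. Trials that cross a boundary at 12 are removed before the second look. With X the count in the first 12 patients and Y the count in the next 12:

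- P(toxicity stop) = P(X ≥ 8) + Σ P(X = s) × P(Y ≥ 15 − s), summed over s = 3 to 7 (smaller s cannot reach 15)
- P(response stop) = P(X ≤ 3) + Σ P(X = s) × P(Y ≤ 7 − s), summed over s = 4 to 7 (larger s cannot stay at or below 7)
- P(stop early) = 1 − [1 − P(response stop)] × [1 − P(toxicity stop)]

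**Toxicity rule at 0.55.** First look: P(X ≥ 8) = 0.3044. Second look: 0.0277×0.0008 + 0.0762×0.0083 + 0.1489×0.0421 + 0.2124×0.1345 + 0.2225×0.3044 = 0.1032. Total 0.3044 + 0.1032 = 0.4077 (unrounded terms).

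**Response rule at 0.5.** First look: P(X ≤ 3) = 0.0730. Second look: 0.1208×0.0730 + 0.1934×0.0193 + 0.2256×0.0032 + 0.1934×0.0002 = 0.0133. Total 0.0863.

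**The method reproduces the plan's own table.** For this block:

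| True response rate | Response rule alone | Toxicity rule alone | Combined | Printed |
|---|---|---|---|---|
| 0.3 | 0.6536 | 0.4077 | 0.7948 | 0.795 |
| 0.4 | 0.2959 | 0.4077 | 0.5829 | 0.583 |
| **0.5** | **0.0863** | **0.4077** | **0.4588** | **0.225** |
| 0.6 | 0.0163 | 0.4077 | 0.4173 | 0.417 |
| 0.7 | 0.0017 | 0.4077 | 0.4087 | 0.409 |

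For the disputed cell: 1 − (1 − 0.0863)(1 − 0.4077) = 0.4588. The 15 cells in the other three blocks also match, so 19 of 20 agree to within 0.0005. A separate simulation of 1,000,000 trials gives 0.4593 for this cell.

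**A floor that does not need independence.** The trial stops whenever the toxicity rule is met, so the probability of stopping early is at least 0.4077 however response and toxicity are related. No cell in this block can be below 0.408.

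**Could simulation error explain it?** With 10,000 trials the standard error is √(0.4588 × 0.5412 / 10,000) = 0.005. The gap is 0.4588 − 0.225 = 0.2338, about 47 standard errors.

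**Could another reading explain it?** For this cell:

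| Reading | Result |
|---|---|
| Look at 12 only | 0.355 |
| Looks at 12, 24 and 36 | 0.511 |
| Looks at 12 and 24, strict response boundary | 0.423 |
| Looks at 12 and 24, strict toxicity boundary | 0.293 |
| Looks at 12 and 24, both strict | 0.247 |

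None gives 0.225. Counting the look at 36 would also break cells that now agree: the first entry in the table, 0.654, would become 0.737.

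**Are the boundaries themselves at fault?** No. Applying the plan's two stopping criteria to its priors (Beta(3, 7) historical, Beta(0.6, 1.4) experimental; margins 0.20 and 0.10; cutoffs 0.90 and 0.85) returns the printed boundaries exactly: 3, 7, 11 for response and 8, 15, 22 for toxicity.

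**The case against.** The arithmetic is not in dispute; what can be argued is how much it matters. Four points deserve weight.

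- The error runs in the safer direction. The design stops a too-toxic regimen more often than the table says, so nobody is falsely reassured.
- Only one output cell is affected. The trial is run from the boundary tables, and no sentence in the section cites 0.225 or bases a choice on it.
- The neighbouring entries, 0.583 and 0.417, are correct and bracket the true value. The entries at response rates 0.6 and 0.7 also describe an active but too-toxic regimen, so an attentive reader can still judge the toxicity rule.
- The maximum of 36 already implies that early means at 12 or 24, so a note saying so is a convenience.

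All four stand and limit the severity. They do not make the printed value correct. It is a stated property that the design does not have, at the combination where the expected response rate meets excess toxicity. The documents do not show how the error arose; a transcription slip would fit an isolated bad cell, but that is conjecture.

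**Conclusion.** The concern holds. The printed 0.225 is about 49% of the value implied by the plan's own rules (0.225 / 0.459). The probability of continuing to 36 patients in this scenario is 1 − 0.459 = 54%, where the table implies 1 − 0.225 = 78%.

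The figure of 0.459 rests on the printed boundaries, the stated independence of response and toxicity, and early stopping meaning a stop at 12 or 24. Agreement with the other 19 cells supports that reading. The conclusion that 0.225 is impossible rests on less: the toxicity boundary alone is enough. This is a correction the plan should make, confined to one cell. It leaves the stopping rules and sample size as they are.

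**What to change.** Check the cell for true toxicity 0.55 and true response rate 0.5 against the simulation output, and replace 0.225 with 0.459 (or the rerun value, which should agree to within about 0.01, two standard errors at 10,000 trials). It would help to add a short note under the table that early stopping counts the looks at 12 and 24 patients and not the final look at 36. The cost is one number and, if wanted, one clause; nothing in the boundaries, priors, sample size or conduct of the trial changes.

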6.3 Phase II

Patients will be enrolled in the phase II portion of this study at the dosing regimen established in the phase 1 portion. Patients will be assessed for response each cycle of therapy.

An additional cohort of 10 patients with myeloma refractory to lenalidomide will be enrolled. This cohort of patients will be treated at the MTD regimen, with lenalidomide 25 mg po days 1-21 on a 28 day cycles and thalidomide 100 mg po daily. The dose of dexamethasone will be 40 mg po weekly.

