Summary statistics will be provided for continuous variables. Frequency tables will be used to summarize categorical variables. Logistic regression will be utilized to assess the effect of patient prognostic factors on the response rate and the toxicity rate. The distribution of time-to-event endpoints will be estimated using the method of Kaplan and Meier. Comparison of time-to-event endpoints by important subgroups will be made using the log-rank test. Cox proportional hazard regression will be employed for multivariate analysis on time-to-event outcomes.

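### Kaplan-Meier is assigned to time-to-event endpoints as a class; for time to best response, progression or death before response is a competing event and needs its own rule

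*Combined protocol and SAP*

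**What the plan says.** Section 4.0 lists "To determine the Time to best response" as a secondary objective in phase 1 and again in phase 2. The Analysis Plan in section 7.0 assigns one estimator to the whole class of such endpoints: "The distribution of time-to-event endpoints will be estimated using the method of Kaplan and Meier". It adds log-rank tests and Cox regression. It does not list the endpoints it means, and no competing-risks method appears anywhere in the document.

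Time to best response is not defined. There is no start date, no analysis set, and no rule for patients who progress, die or leave before a best response is recorded.

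The conduct sections determine what happens to those patients:
- Section 6.3.1: "Patients who progress will be removed from therapy".
- Section 6.7, Follow-Up: "Treatment is to be continued and patients will be followed until progression of disease".
- Section 6.3.1 also provides that patients already in CR, VGPR or PR "may elect to stop treatment at any point after cycle 2 and proceed to stem cell mobilization and transplantation". Others "may receive up to 8 cycles of the combination therapy".
- A footnote to the response criteria table at the end of the document requires the confirming assessments to come before any new therapy.

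How many patients respond is a separate endpoint. The phase 2 primary objective is "To determine the overall (CR + VGPR+ PR) response rate of the combination after 4 cycles of therapy".

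**The concern.** Kaplan-Meier needs an event time or a censoring time for every patient. For a patient who progresses without responding, the obvious time to enter is the date of progression, because disease follow-up stops there. Censoring at that date assumes that the patient keeps the same chance of responding later as those still on treatment. Under this protocol that chance is nil: the patient is off therapy, and a response after new therapy cannot count. Progression, like death, therefore prevents the event.

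With such patients censored, 1-KM estimates response in a hypothetical setting without progression. It lies above the proportion who actually respond, and the gap widens as more patients progress early. A reader of the time-to-response curve could take away a higher and faster response than the trial observed.

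**Working it through.** The documents give no figure for time to best response, so there is nothing to reproduce. What follows is an illustration for time to **first** response, which is simpler than best response.

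**Inputs**
- True proportion responding, pR = 50%: the expected response rate in section 7.0, Phase II design.
- Horizon T = 8 cycles: the maximum length of combination therapy in section 6.3.1. Response is assessed every cycle (section 6.3: "Patients will be assessed for response each cycle of therapy").
- Proportion progressing or dying before response, pP: not in the documents; assumed 5% to 40%.
- Constant hazards hR (response) and hP (progression first): assumed.

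**Formulas**
- (hR + hP)T = -ln(1 - pR - pP)
- hR·T = (hR + hP)T × pR/(pR + pP)
- 1-KM at T, with progressors censored = 1 - exp(-hR·T)
- Kaplan-Meier median = T × ln 2/(hR·T)
- The true cumulative incidence at T is pR by construction, so the true 50% point is 8.0 cycles.

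Worked case, pP = 20%: -ln(0.30) = 1.204; × 0.5/0.7 = 0.860; 1 - exp(-0.860) = 57.7%; median 8 × 0.693/0.860 = 6.45 cycles.

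| pP (assumed) | hR·T | 1-KM | Excess, points | KM median, cycles (true 8.0) |
|---|---|---|---|---|
| 5% | 0.726 | 51.6% | 1.6 | 7.64 |
| 10% | 0.764 | 53.4% | 3.4 | 7.26 |
| 20% | 0.860 | 57.7% | 7.7 | 6.45 |
| 30% | 1.006 | 63.4% | 13.4 | 5.51 |
| 40% | 1.279 | 72.2% | 22.2 | 4.33 |

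The 1-KM column does not depend on T. With a 4-cycle horizon the medians halve. At a 30% response rate the excess over the same range of pP is 0.9 to 10.3 points.

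**A 36-patient example** (36 is the phase II sample size; the event times are invented). Responses: 4, 6, 4, 2, 1, 1 at cycles 1 to 6, 18 in all. Progression first: 2, 3, 2, 2, 0, 1 at cycles 1 to 6, 10 in all. Eight patients are stable to cycle 8.
- Progressors censored: survival = (32/36)(24/30)(17/21)(13/15)(10/11)(9/10) = 0.408. So 1-KM = 59.2%, and the curve crosses one half at cycle 4.
- Progressors kept in the risk set to cycle 8 as non-responders, which here equals the cumulative incidence: 18/36 = 50.0%, reached at cycle 6.
- Responders only: 10 of 18 have responded by cycle 2, so the median is 2 cycles; the curve reaches 100% by construction.

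The same data thus give medians of 4, 6 or 2 cycles, and the plan does not say which analysis applies.

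**The case against.** The strongest reply is that the bias is not written into the plan. The Kaplan-Meier sentence does not name time to best response, and no censoring rule is given. The bias disappears if progressors stay in the risk set as non-responders, and it does not arise in a responders-only summary, which the plan's general provision for summary statistics could cover. This stands: censoring at progression is an inference from sections 6.3.1 and 6.7. It does not remove the point, because Kaplan-Meier is the only estimator the plan names for such endpoints and it states neither alternative.

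The illustration also models first response. Best response is known only in retrospect, can deepen through later cycles, and can be cut short by a transplant exit. The figures therefore show direction and order of size; they do not measure the bias for this endpoint.

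The upper end of the range is loosely anchored. Section 1.3.5 gives a median time to progression of 11.1 months on lenalidomide plus dexamethasone. Four cycles are 112 days, or 3.68 months. With exponential times, 1 - 0.5^(3.68/11.1) = 21% progress by then. The 1-year progression-free survival of 48.6% in section 1.3 gives 1 - 0.486^(3.68/12) = 20%. Both include patients who had already responded. The 40% case is nearer the dexamethasone-alone arm: median 4.7 months, 1 - 0.5^(3.68/4.7) = 42%. At 20% or less the excess is at most about 8 points, below the 13-point half-width implied by the plan's 0.26-wide credible interval. This is a fair reason to give weight to the lower rows over four cycles. Over eight cycles (7.36 months) the 11.1-month figure gives 1 - 0.5^(7.36/11.1) = 37%, again counting responders, so the higher rows cannot be dismissed.

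**Conclusion.** The point holds in a limited form. The plan gives Kaplan-Meier to time-to-event endpoints as a class and leaves the handling of patients who progress or die before responding unstated for time to best response. If they are censored, 1-KM overstates the cumulative incidence of response. In the illustration the excess is about 2 to 8 points when 5-20% progress first and about 22 points when 40% do. This rests on constant hazards, a true 50% response, time to first response, and progression shares that are assumed.

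A reader might infer more than the documents support:
- **That the trial will overstate its response rate.** It will not. The primary endpoint is a proportion after 4 cycles, monitored by beta-binomial rules; neither it nor the stopping boundaries use this curve.
- **That Kaplan-Meier is wrong for every endpoint.** For PFS, progression is the event and Kaplan-Meier is standard.
- **That a median will always appear even when fewer than half respond.** It can: with 40% responding and 40% progressing first, 1 - exp(-1.609 × 0.5) = 55%. It need not: with 30% responding and 40% progressing first, 1-KM reaches only 40%.

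Severity is minor: this is a secondary, descriptive endpoint in an open-label study without a control arm.

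**What to change.** Add two or three sentences to the Analysis Plan in section 7.0:
- Define time to best response: the start date, the date that counts as the event, and the window over which best response is judged.
- Estimate it in all treated patients by the cumulative incidence function (Aalen-Johansen), with progression and death before response as competing events.
- State how patients who leave for transplant enter the analysis.
- Report any median time among responders only, and label it so.
- Keep Kaplan-Meier for PFS.

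The cost is a few lines of text and standard software. Sample size, stopping rules and patient care do not change. The downside is that the reported curve will be lower than 1-KM with progressors censored.
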